After the child has a positive TB screen the appropriate healthcare worker, such as the treating clinician or TB nurse, will begin filling out their section designated for requesting health workers on the CaP TB Pediatric TB Form, pre-printed with sequential numbers in each country using the Form. For children screened at HIV clinics or during contact tracing, this section will be directly filled for all children screened, irrespective of the presence of signs or symptoms or TB. This part of the form contains identifying information of the pediatric patient, contact information and identifies if the patient is exhibiting sign or symptoms concerning of TB, and if so which ones. If signs or symptoms of TB are identified, the facility TB nurse or focal point will then detach the last copy of the form (the pink form) and keep this form at the facility. The remaining three carbonated copies of the CaP TB Pediatric TB form will then be used as a referral form for sample collection and TB testing. The patient or patient's caregiver will be sent with the remaining three copies of the carbonated form to have a specimen collected. The healthcare worker collecting the sample will then fill out the section "To be filled at specimen collection site." This section contains information on the date of collection and type of specimen collected. The remaining three copies of the carbonated form, along with the specimen will be sent to the laboratory for specimen processing. The laboratory staff will fill out the section "To be filled by lab personnel." This section will contain information about the type of testing performed, the date of testing and the results of testing. The laboratory staff will detach one copy (the blue form) and keep this at the laboratory. The remaining two copies of the CaP TB Pediatric TB form, which contains the patient's results, will then be returned to the requesting facility. The requesting facility/treatment unit will then complete the section "To be filled by TB treatment unit." This section will contain additional information, including results of chest X-ray and if the patient was diagnosed based on clinical symptoms with or without radiologic signs. This section will also contain information about treatment initiation or the facility to which the patient was referred for treatment initiation as well as the patient's TB treatment register number. The first (white) page will be kept at the requesting facility for their records.

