The CaP TB Pediatric TB Form will also be used for referral for an initiation of TB preventive therapy, primarily during contact tracing or screening at HIV clinics. The relevant healthcare worker will fill the section "To be filled by requesting health worker" and the section "To be filled during contact tracing and in HIV clinic only." These sections contain identifying information of the pediatric patient, contact information and information on eligibility for TB preventive therapy. If the child was identified at the HIV clinic, the healthcare worker keeps the last copy (pink) and the child/caregiver will bring with him/her the three remaining copies of the carbonated form and gives them to the unit initiating PT. If the child was identified through

contact tracing in the household, the community health worker (CHW) gives the last copy (pink) to the patient or patient’s caregiver and the CHW brings the remaining 3-copy form to the TB unit. When the patient presents to the facility for TB preventive therapy initiation, the healthcare worker initiating TB preventive therapy will complete the section “To be filled by HCW providing PT.” This section contains information on TB preventive therapy initiation, date of initiation and the patient’s preventative therapy register number. In the event that the initiation date is not recorded, an EGPAF data collector will be responsible for following up with the entry point or facility providing TB preventative therapy. Upon completion of the form, one copy will remain at the facility (1st page) and the data entry copy (2nd page) will be transferred to the EGPAF office for entry into the project database.

CaP-TB data collector will ensure timely data collection and reporting from all CaP-TB sites. This copy is the project’s data collection form. The form that data collectors will be collecting has all identifying information for the patient blocked out, except the child ID (if any), the TB treatment register number (or TB preventive therapy register number), the sex, and the date of birth to protect patient confidentiality.

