Data collectors will also collect the ICF tools from the various entry points and collate aggregated data using an ICF data abstraction tool (Attachment B: Pediatric TB Intensified Case Finding Screening Data Abstraction Tool) which will be entered directly into the electronic data entry form. Data collectors will also extract information, such as date of treatment completion, from the TB treatment and TB preventive therapy registers. In the pilot phase (years 1 and 2), data collectors will visit sites frequently for data extraction (approximately every 4-6 weeks). In the expansion phase (years 3 and 4), data collectors will visit sites less frequently for data extraction (approximately every 1-3 months).

Data collection when the project-specific data collection tools are not used

If the CaP TB Pediatric TB Form is not completed or the country does not support use of the ICF Tool and/or CaP TB Pediatric TB Form for all or part of the data collection, data collectors will extract data from relevant sources such as existing registers and logs as in the pre-intervention baseline data collection phase. An indicator mapping exercise will first be conducted to identify the location and source of all required data. This indicator mapping exercise is expected to inform the data collection process which will take place on site, at the project facility. Data will be extracted from the source register or log and, recorded in the baseline data abstraction tool and entered into the CaP TB Database Entry Tool developed for pre-and post-intervention data. Only data required for the project M&E activities will be extracted and will be the same data collected through the CaP TB Pediatric TB Form. EGPAF will closely monitor data collection activities of any country team that cannot use the CaP TB Pediatric TB Form to ensure high quality data is collected. All data collection tools and processes will be approved by the in-country IRB.

A. [Table 1. Indicator Outcomes and Data Sources](#)

This table presents an example of data sources. Specific data sources may vary from country to country. All country-specific data sources will be approved for data extraction by the local IRB.

Primary Outcomes	Data Source Pre-Intervention	Data Source Post-Intervention

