Number and proportion of children screened for TB among clinic attendees	TB screening logbooks/registers	Pediatric TB Intensified Case Finding Screening Tools and Clinic attendance registers And/or TB screening logbooks/registers
Number and proportion of presumptive pediatric TB cases identified among children screened for TB	TB screening logbooks/registers Presumptive TB registers	CaP TB Pediatric TB Form And/or TB screening logbooks/registers
Number and proportion of presumptive TB cases referred for lab-based TB diagnosis	TB screening logbooks/registers or Presumptive TB registers	CaP TB Pediatric TB Form And/or TB screening logbooks/registers, Presumptive TB registers
Number and proportion of pediatric (0-14 years) presumptive TB cases who are tested with Xpert	TB diagnostic logbooks/registers or Xpert logbooks/registers	CaP TB Pediatric TB Form And/or TB diagnostic logbooks/registers or Xpert logbooks/registers
Number and proportion of pediatric TB cases diagnosed with active TB disease among presumptive TB cases	Presumptive TB registers and TB registers	CaP TB Pediatric TB Form And/or TB registers/logbooks
Time between when a child is identified as a presumptive TB case and when the child is diagnosed with TB	Presumptive TB registers, TB registers/logbooks	CaP TB Pediatric TB Form And/or Presumptive TB registers, TB registers/logbooks
Number and proportion of pediatric TB cases started on DS-TB treatment	TB registers/logbooks	CaP TB Pediatric TB Form And/or TB registers/logbooks
Time between when a child is identified as a presumptive TB case and when the child is initiated on TB treatment	Presumptive TB registers, TB registers/logbooks	CaP TB Pediatric TB Form And/or

		Presumptive TB registers, TB registers/logbooks
Number and proportion of pediatric DS-TB cases who achieve treatment success	TB treatment register	TB treatment register
Number and proportion of all TB index cases for whom successful contact tracing has been done	TB registers/logbooks Contact tracing forms and registers if available	CaP TB Pediatric TB Form and TB register And/or TB registers/logbooks Contact tracing forms and registers if available
Number and proportion of pediatric household contacts who are negative to TB screening	TB registers/logbooks Contact tracing forms and registers if available	CaP TB Pediatric TB Form And/or TB registers/logbooks Contact tracing forms and registers if available

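### Forms issued are never reconciled with forms received, so children lost before testing, diagnosis or preventive therapy may be missing from form-based post-intervention denominators

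*Combined protocol and SAP*

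**What the plan says.** The form's path is set out in protocol section VI, under the use of project-specific tools.

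- **Presumptive TB.** After a positive screen the facility is to "detach the last copy of the form (the pink form) and keep this form at the facility". The caregiver "will be sent with the remaining three copies of the carbonated form to have a specimen collected". Those copies then go to the laboratory with the specimen. The laboratory keeps the blue copy and two copies return to the requesting facility.
- **Preventive therapy, HIV clinic.** The clinic keeps the pink copy and the caregiver takes the other three to the unit that starts therapy.
- **Preventive therapy, household contacts.** The family gets the pink copy and "the CHW brings the remaining 3-copy form to the TB unit".
- **Transfer of data.** "Upon completion of the form, one copy will remain at the facility (1st page) and the data entry copy (2nd page) will be transferred"; its destination is the project office. Section VI identifies this page as the project's data collection form, and Annex A says the database entry tool mirrors the second page.
- **Numbering.** Forms are "pre-printed with sequential numbers in each country using the Form".
- **Fallback.** "If the CaP TB Pediatric TB Form is not completed or the country does not support use of the ICF Tool" (or of the Form itself), data collectors go to existing registers and logs, as at baseline.

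Table 1 gives the Form, and/or registers, as the post-intervention source for most cascade indicators. Section IX compares pre- and post-intervention proportions by relative risk or risk difference, with Z-tests.

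**The concern.** A presumptive child who never reaches specimen collection should count as a failure in the proportions tested and diagnosed. An eligible child in an HIV clinic who never reaches the preventive-therapy unit should count as a failure in the proportion started. On both pathways the page that feeds the database leaves with the family, so the event that makes the child a failure can also remove the record.

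Loss between steps of the cascade is what the project sets out to reduce. If such losses are recorded at baseline but partly unrecorded after launch, better linkage cannot be told apart from missing paper, and the error favours the project. The exposed proportions are primary-objective indicators, and one of them, starting preventive therapy among eligible children, is also a key indicator in section V.A.

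**Working it through.** **1. Which page travels.** The first page is white and stays at the requesting facility. The second is yellow (section X) and is the data-entry copy. The laboratory keeps blue, and the last copy is pink. Once pink is detached, the three copies carried are white, yellow and blue, so the data-entry page is among them. A child who goes no further leaves only a pink copy on file. No section makes the pink copy a data source, checks gaps in the form numbers, or says what completion means for such a child.

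**2. Would another procedure notice the missing form?**

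- The register fallback in section VI applies when a form is not completed. Nothing alerts a collector that a form was issued and never came back.
- Quality rounds (section IX.A) look for omissions, but at randomly selected sites and with the aim of proper form completion. The database check samples forms that exist.
- Parallel recording in national registers (end of section X) preserves information, but no step matches it to issued forms.
- The follow-up of an unrecorded preventive-therapy start concerns one missing date.
- The screening (ICF) tool carries no identifiers, is collated in aggregate, is replaced by the Form in HIV clinics and contact tracing, and is not a Table 1 source for presumptive cases.

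**3. Before against after, by Table 1 row.**

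| Proportion | Baseline source | Post-intervention source |
|---|---|---|
| Diagnosed among presumptive | Presumptive and TB registers | Form and/or TB registers/logbooks |
| Tested with Xpert | Diagnostic or Xpert logbooks | Form and/or the same logbooks |
| Started preventive therapy among eligible | Preventive-therapy register | Form and/or the same register |

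Only the first row names, at baseline, a register of presumptive children and then omits it after launch.

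**4. Size.** The documents give no form-loss rate, so there is no planned figure to reproduce. Let p be the true proportion tested, equal in both periods, and f the share of untested children's forms that are lost and not recovered. Both are assumptions, as is a complete baseline denominator.

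Observed post-intervention proportion = p / [p + (1 − p)(1 − f)]; spurious relative risk = observed / p.

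Example: p = 0.7, f = 0.25 gives 0.7 / (0.7 + 0.3 × 0.75) = 0.7 / 0.925 = 0.757, and 0.757 / 0.7 = 1.08.

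| p | f = 10% | f = 25% | f = 50% |
|---|---|---|---|
| 0.5 | 0.526 (RR 1.05) | 0.571 (RR 1.14) | 0.667 (RR 1.33) |
| 0.7 | 0.722 (RR 1.03) | 0.757 (RR 1.08) | 0.824 (RR 1.18) |
| 0.9 | 0.909 (RR 1.01) | 0.923 (RR 1.03) | 0.947 (RR 1.05) |

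For diagnosed among presumptive, let L be the share of presumptive children lost undiagnosed. The spurious relative risk is 1 / (1 − L × f). At f = 25% it is 1.03, 1.08 and 1.14 for L = 0.1, 0.3 and 0.5.

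For presumptive among screened, a form-based numerator shrinks and the relative risk is 1 − L × f, a deflation. At L = 0.3 and f = 25% it is 1 − 0.075 = 0.925.

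If forms of tested children are also lost, at rate g, the observed proportion is p(1 − g) / [p(1 − g) + (1 − p)(1 − f)]. With g = f this returns p, so inflation requires f > g.

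**5. Effect on the Z-test.** Table 3 expects at least 5 presumptive children per clinic and up to 200 baseline sites: 200 × 5 = 1,000. Assume 1,000 presumptive children in each period (925 recorded after launch), p = 0.7, f = 25%, two-sided 5% level and independent children. The test then rejects about 80% of the time with no true change. At f = 10% it rejects about 18% of the time.

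**The case against.** The strongest reply is that the plan has several overlapping records: the pink copy on site, sequential numbers, continuing registers, the fallback for incomplete forms, and quality rounds that look for omissions. A child lost before testing does have an incomplete form, so a diligent collector could recover that child. The ICF tool also gives an aggregate count of symptomatic children outside HIV clinics and contact tracing. This stands in part. The means of recovery exist, and the loss is possible rather than established. What is missing is any step that uses these records to find an unreturned form.

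Other limits also stand:

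- The transfer sentence sits in the preventive-therapy paragraph. Applying it to testing and diagnosis is an inference, though the presumptive pathway describes no other route for that page. The sentence does not say that transfer happens only on completion.
- For "Number and proportion of pediatric (0-14 years) presumptive TB cases who are tested with Xpert", the baseline row names no presumptive register either, so a complete baseline denominator is not shown. The same doubt applies to starting preventive therapy among eligible children, whose baseline source is the preventive-therapy register alone.
- For household-contact preventive-therapy referrals, the community health worker carries the form.
- A form lost after the laboratory step, or for a child diagnosed clinically, removes a success as well as a denominator entry, which weakens the bias.

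**Conclusion.** The gap is real but narrow. As written, the plan allows children with unreturned forms to be missing from form-based post-intervention denominators, and it has no step that would reveal this. Proportions with presumptive or eligible children as denominator are liable to inflation. The pre/post asymmetry is clearest for diagnosed among presumptive.

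The size cannot be determined from the documents. With 50% to 90% truly tested in both periods and 25% of untested children's forms lost, the spurious relative risk is about 1.03 to 1.14. This assumes a complete baseline, no loss of tested children's forms, and no recovery of the lost ones.

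A reader might infer that such children do drop out and that post-intervention proportions in general are inflated. The documents do not support that. The loss rate is unknown and the safeguards would reduce it. Counts of children diagnosed are not inflated. Treatment success and preventive-therapy completion come from registers in both periods. Presumptive among screened would be deflated if form-based. This is a cheap improvement to make, not evidence that the results are biased.

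**What to change.** In section VI and the data-management procedures:

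1. At each scheduled visit, reconcile the pre-printed numbers on retained pink copies against the data-entry pages received, for the presumptive pathway and for HIV-clinic preventive-therapy referrals.
2. For a form not returned within a fixed interval, check the presumptive, TB and preventive-therapy registers. Then enter the child from the pink copy, using de-identified variables only because that copy carries identifying details.
3. Code steps with no record as not done/unknown, and keep the child in all downstream denominators.
4. In Table 1, list presumptive TB registers as a post-intervention source for diagnosed among presumptive.
5. Report forms issued against forms received, by site.

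The cost is about one paragraph of protocol text and slightly longer visits. Forms are already numbered, and collectors already visit about every 4 to 6 weeks in the pilot phase and every 1 to 3 months in expansion. Post-intervention proportions may look less favourable.

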2. Country-Level Activities

EGPAF and SAATHII have strong expertise in implementing innovative service delivery models and will provide training, supportive supervision, job aids, and standard operating procedures (SOPs) to health care workers who are engaged in the care of pediatric patients at CaP TB facilities. The goal of these activities is to support the strengthened uptake of current recommendations on TB screening, diagnosis and treatment as well as allow for decentralization and integration of pediatric TB care. CaP TB will also provide training to strengthen completion of TB registers, and may develop other M&E tools to improve the documentation of pediatric TB. EGPAF and SAATHII will also assess and provide SOPs and infrastructure upgrades to improve infection control. EGPAF and SAATHII will support innovations to improve service delivery including creating facility-specific TB champions to monitor service quality, regular performance feedback to facilities, and work with civil society to identify areas to improve care.

Specific packages of activities will vary by country and will be determined based on (1) national policies and guidelines; (2) planned and existing activities supported through other efforts; and (3) country-specific pediatric TB burden and barriers and bottlenecks. For Country Submission- refer to country specifics.

In general, country-level activities will include:

- Decentralizing and integrating delivery of pediatric TB care (diagnosis, treatment (where feasible), and prevention) into MNCH, HIV, nutrition and other key pediatric entry points at the facility level;
- Supporting community-level contact tracing and screening of pediatric contacts for index patients with active TB and where feasible according to MOH guidance, initiation of preventative TB therapy at the community level;
- Documenting and generating evidence for innovative models of care through M&E;
- Strengthening data systems through support for improved use of current registers as well as introduction of new data tools where gaps exist (e.g. for tracking of TB preventative therapy completion in some countries);
- Supporting rapid uptake through trainings, site monitoring and mentorship and strengthening sample transport and referral systems of new diagnostics and medicines that are included in WHO guidelines and are either included in country guidelines or are in the process of being incorporated into national guidance, such as:

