In each site, trained data collectors will retrospectively extract data from appropriate registers, logs, and in some cases patient files, for a period of 12 months starting 6 or more months before the start date of data extraction. This time frame has been selected in order to allow to accurately measure indicators on treatment completion for both drug-sensitive TB treatment and preventive therapy (treatment lasts 6 months in both cases). In certain cases, the data sampling frame will start more than 6 months before the data extraction if CaP TB interventions had started during the sampling frame. Thus the sampling frame was chosen so that the end date of retrospective pre-intervention data abstraction would be before the start of any intervention to ensure that the baseline data was not affected by the early activities. For some indicators, baseline data will not be available in existing registers or logbooks. Data collectors will extract data from all pediatric entry points within the facility, including MNCH, HIV, nutrition and other relevant pediatric health care entry points. Only required variables will be abstracted and entered into the password-protected computers. Data with the patient date of birth (DOB), patient ID (if any), TB treatment ID and preventive treatment ID will be collected. The patient ID (if any), TB treatment ID and preventive treatment ID will all be encrypted before being uploaded into the CaP TB Database Entry Tool. DOB will be abstracted in order to facilitate tracking across registers if needed, as well as for data quality assurance purposes. This information will only be used to link registers. Only de-identified patient data will be abstracted into our global project

database. No other unique identifiers such as contact details of the children or their caregiver will be abstracted from the registers. Data from included pediatric patients will be extracted from the registers and recorded in the CapTB Baseline Data Abstraction form from where the data will be entered into a CaP TB Database Entry Tool (Excel-based and/or Web/mobile App-based) developed for pre-and post-intervention data , in a password protected computer and/or Android device (See Annex A: CapTB Information System).

The target population for the pre-intervention assessment is the records of any pediatric patient (0-14 years of age) who attend one of the sub-set of pilot sites in any of the 10 CaP TB countries who receive TB services. TB services include:

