Location of activity	10-20 purposively selected pilot sites in each country, for a total of up to 200 sites across all ten countries. Sites will be selected based on geography (urban vs rural) and health facility level. We estimate that 12 months of data will be sufficient to appropriately assess the indicators from the primary objectives under standard of care conditions. The overall sample size in each country and per facility sample size will vary greatly by facility level, pediatric population density and indicator. However, we estimate that we will collect data for at least 5 children with presumptive TB in each clinic.	Up to 70 sites in each country for a total of up to 700 sites across all ten countries.
Timing	15-20 CaP TB pilot sites in each country	All CaP TB sites across 10 countries (up to 700 sites)
Method	Retrospective data collection will occur upon site selection. It is estimated that the retrospective data collection for all sample project sites in a given country will take six to ten weeks.	Data collection will begin when each site begins implementation of CaP TB and will go on through the end of the project
	Data abstraction of TB registers, HIV registers, PMTCT registers and other relevant logbooks	Data abstraction from clinic attendees registers, Pediatric TB Intensified Case Finding Screening Tool, CaP TB Pediatric TB Form, TB treatment register, TB preventive therapy register and other TB registers and logbooks as needed

Informed Consent documents	Informed consent waiver to be requested	Informed consent waiver to be requested
Data collection tool	Baseline data abstraction tool	Pediatric TB Intensified Case Finding Screening Data Abstraction Tool and CaP TB Database Entry Tool

IX. Data Management and Statistical Analysis

Quantitative de-identifiable data extracted from the source documents will be coded and entered directly into a database that will be designed specifically for the project and stored on a secure cloud server. Data will be aggregated in the database and entered into an electronic dashboard that will demonstrate the data standardized to project indicators and data elements. Frequencies will be calculated for each response and descriptive statistics will be calculated.

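### The Xpert-testing indicator is read from on-site logbooks at baseline but from a form that brings the laboratory result back after launch, so off-site tests may be under-counted before and better captured after

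*Combined protocol and SAP*

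**What the plan says.** Testing with Xpert among presumptive children is indicator d of the primary objective (Section II.B.1). Secondary objective a compares the indicators with baseline in a subset of sites.

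- **Baseline source.** Table 1 names "TB diagnostic logbooks/registers or Xpert logbooks/registers". Section V.A places the work at the facility: "In each site, trained data collectors will retrospectively extract data from appropriate registers, logs, and in some cases patient files", and "Data collectors will extract data from all pediatric entry points within the facility". The baseline method row of Table 3 lists "Data abstraction of TB registers, HIV registers, PMTCT registers and other relevant logbooks"; Xpert or laboratory logs are not named there. No visit to an outside laboratory is described.
- **Source after launch.** Table 1 names "CaP TB Pediatric TB Form And/or TB diagnostic logbooks/registers or Xpert logbooks/registers". Section VI explains that copies of the Form "along with the specimen will be sent to the laboratory for specimen processing", and that the remaining copies, "which contains the patient's results, will then be returned to the requesting facility".
- **Off-site testing.** Section IV.A.2 includes "strengthening sample transport and referral systems of new diagnostics" among the project activities. This implies that some specimens are tested away from the site that requests the test. The share is not given.
- **Analysis.** Section IX compares periods by a ratio or difference of proportions with Z-tests. It gives no restriction, adjustment or sensitivity analysis for a change of data source.

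**The concern.** The two periods may not capture a referred specimen in the same way. After launch the Form ties the laboratory result to the facility that asked for it. At baseline no equivalent rule is stated. If the logbooks read at a sending site do not record results returned from elsewhere, a child tested off site can go unseen at baseline and be seen later, with no change in practice.

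Table 1 also lists presumptive TB registers at baseline for the neighbouring rows on identification, referral, diagnosis and turn-around time, but not for the Xpert row. The requesting site's own record is therefore not named as a source for this numerator.

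Uptake of Xpert is something the project sets out to raise, partly through better specimen transport. An artefact of this kind would be largest where specimens travel, which is also where a real gain is expected. The two could not be separated afterwards.

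**Working it through.** The documents give no Xpert proportion, off-site share, alpha or sample size for this comparison, so there is no stated figure to reproduce. The calculation below only shows how the artefact scales.

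**Assumed inputs**

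- p: true proportion of presumptive children tested, the same in both periods.
- s: share of tested samples absent from the baseline logbooks as abstracted, with those children counted as untested.
- f: fraction of those missing samples that the Form recovers after launch. f = 0 means that the same logbooks serve both periods.

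**Formulas**

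- Measured baseline = p(1 − s)
- Measured after launch = p[1 − s(1 − f)]
- Spurious relative risk = [1 − s(1 − f)] / (1 − s), which does not depend on p

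**Spurious relative risk with no true change**

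| s | f = 1 | f = 0.5 | f = 0 |
|---|---|---|---|
| 10% | 1.11 | 1.06 | 1.00 |
| 20% | 0.80 missing share restored: 1.00/0.80 = 1.25 | 0.90/0.80 = 1.125 | 1.00 |
| 30% | 1.43 | 1.21 | 1.00 |
| 50% | 2.00 | 1.50 | 1.00 |

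**What the Z-test would do.** Table 3 allows up to 200 baseline sites and expects at least 5 presumptive children per clinic: 200 × 5 = 1,000. Take 1,000 in each period, p = 30% and s = 20%.

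- f = 1: 24% against 30%. Pooled proportion 0.27; standard error √(2 × 0.27 × 0.73 / 1,000) = 0.0199; Z = 0.06 / 0.0199 = 3.02. The chance of significance at an assumed two-sided 0.05 is 86%.
- f = 0.5: 24% against 27%. Pooled proportion 0.255; standard error √(2 × 0.255 × 0.745 / 1,000) = 0.0195; Z = 0.03 / 0.0195 = 1.54. The chance is 34%.
- With s = 10%, the chances are 32% (f = 1) and 11% (f = 0.5).

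The 1,000 multiplies the largest number of sites by the smallest number of children per clinic; 100 sites (10 per country) would give 500. Children are treated as independent, with no allowance for clustering by site.

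**The case against.** A reader might infer that every off-site test counts as untested before launch and tested after, so that the baseline numerator is simply wrong. The documents do not support that.

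- They do not say where the baseline logbooks are held, that a diagnostic logbook omits returned results, or that a child without an entry counts as untested. Section V.A also allows patient files, which could hold a returned result.
- Table 1 is presented as an example that may differ by country. Where the Form is not supported or not completed, Section VI sends data collectors back to registers and logs as at baseline. Both periods then share the limitation, and the artefact is nil.
- Under-capture at sending sites may be partly offset. If a sampled hosting site's logbook is counted row by row, a referred specimen can appear there. In the example with 1,000 children, 240 recorded tests plus the 60 missing ones found at sampled hosts give 300/1,000 = 30%, and no artefact. Specimens sent in by facilities outside the sample would raise the baseline further.

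A reader might also infer that hosting sites will score above 100%, or that repeat tests on one child will inflate the count. That requires counting raw logbook rows, which no section prescribes. The indicator is defined on presumptive children, Section V.A collects identifiers and dates of birth to link registers, and Section X refers to counting unique patients.

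On weight, Xpert testing is not among the four key indicators in Section V.A, and the pre/post comparison is a secondary objective.

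These points limit what can be said about size and consistency. They do not remove the gap. Nothing in the plan says how a baseline test done elsewhere is credited, and the offset at hosting sites would depend on the row-by-row counting that the plan's linkage provisions point away from.

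**Conclusion.** The concern holds in a limited form. Where specimens are tested off site and the Form is used, following the plan can produce an apparent rise in Xpert testing without any change in practice. Section IX has nothing to detect or remove it. Where under-capture at sending sites is the main error, the bias favours the project.

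The size is unknown. The range from 1.00 to 1.25 for s = 20% rests on assumed values of s and f, equal testing in both periods, and missing entries being read as untested. Larger ratios need a larger off-site loss at baseline together with near-complete recovery by the Form, and the documents establish neither. The pooled result may also mix countries with and without the artefact, because sources may differ by country.

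**What to change.** For indicator d, state in Table 1 and the abstraction procedure that each test is credited to the requesting facility and that children, not tests, are counted, in both periods.

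Record for each site which source is used in each period. Run the pre/post test only on sites where off-site results can be captured in the same way before and after: a common logbook or register, patient files, or on-site Xpert. Classify results that cannot be linked as unknown, not as untested. Report the other sites descriptively.

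The presumptive TB register, or a hosting site's logbook filtered by requesting facility, should be used only where it is confirmed to record the Xpert result or the requesting facility. The documents describe neither field.

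The change takes a few lines of text plus a check of sources at each site, which can be part of the indicator mapping already planned in Section VI for places where the project tools are not used. The downside is fewer sites in the pre/post comparison of this one indicator.
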